### **5.5.1. Investigational Medicinal Product Return or Disposal**

At the beginning of the study, the study monitor will evaluate the study center's study drug disposal procedures and provide appropriate instruction for return or destruction of unused study drug supplies. If the site has an appropriate Standard Operating Procedure (SOP) for drug destruction, the site may destroy used and unused study drug supplies performed in accordance with the site's (hospital/pharmacy) SOP. If the site does not have acceptable procedures in place for drug destruction, arrangements will be made between the site and Gilead Sciences (or Gilead Sciences' representative) for return of unused study drug supplies. A copy of the site's SOP will be obtained for central files. Where possible, study drug will be destroyed at the site.

Upon study completion, a copy of the Investigational Drug Accountability records must be filed at the site. Another copy will be returned to Gilead Sciences. If drug is destroyed on site, the investigator must maintain accurate records for all study drug kits and/or bottles destroyed. Records must show the identification and quantity of each unit destroyed, the method of destruction, and person who disposed of the drug. All study drug records must be maintained at the site and copies must be submitted to Gilead Sciences at the end of the study.

## 6. STUDY PROCEDURES

The study procedures to be conducted for each subject enrolled in the study are presented in tabular form in [Appendix 2](#) and described in the text that follows.

The investigator must document any deviation from protocol procedures and notify the sponsor or contract research organization (CRO).

### 6.1. Subject Enrollment and Treatment Assignment

Entry into screening does not guarantee enrollment into the study. In order to manage the total trial enrollment, Gilead, at its sole discretion, may suspend screening and/or enrollment at any site or trial-wide at any time.

### 6.2. Pretreatment Assessments

**Prior** to the conduct of any screening procedures, each candidate must sign an Informed Consent Form. Consent is to be obtained in accordance with regulatory and local Ethics Committee requirements.

#### 6.2.1. Screening Visit

Subjects will be screened within 45 days before randomization/enrollment to determine eligibility for participation in the study.

- Review of inclusion/exclusion criteria
- Obtain medical history (including HBV disease and treatment history)
- Review concomitant medications
- Complete physical examination
- Vital signs
- Body weight and height
- 12-lead ECG (Subjects must rest quietly in the supine position for a minimum of 5 minutes prior to the recording)
- Sample Collection for:
  - Safety laboratory tests (hematology, chemistry, and coagulation)
  - Serology testing to exclude HCV, HDV, and HIV infection

- Quantitative plasma HBV DNA
- Quantitative serum HBsAg, CCI [REDACTED]
- Qualitative HBV serology (HBeAg [reflex HBeAb if HBeAg is negative] and HBsAg [reflex HBsAb if HBsAg is negative])
- HBV viral sequencing samples (resistance surveillance)
- Estimated creatinine clearance (using the Cockcroft-Gault method)
- Other screening laboratory tests: urinalysis, urine drug screen, and serum  $\beta$ -hCG (females of child bearing potential only)

Record any serious adverse events and all adverse events related to protocol mandated procedures occurring after signing of the consent form.

Subjects meeting all of the inclusion criteria and none of the exclusion criteria will return to the clinic within 45 days after screening for randomization or enrollment into the study.

From the time of obtaining informed consent through the first administration of investigational medicinal product, record all serious adverse events (SAEs), as well as any adverse events related to protocol-mandated procedures on the adverse events case report form (eCRF). All other untoward medical occurrences observed during the screening period, including exacerbation or changes in medical history are to be captured on the medical history eCRF. See Section 7 Adverse Events and Toxicity Management for additional details.

#### **6.2.2. Baseline Assessments (Day 1)**

All baseline tests and procedures must be completed prior to the receipt of the first dose of study drug. Subjects screened within 45 days before Baseline will be eligible to participate in the study. Initiation of treatment with study drug should take place on the day of the Baseline Visit.

- Review of inclusion/exclusion criteria and confirm medical history
- Complete Physical Examination including body weight
- Vital signs
- 12-lead ECG (Subjects must rest quietly in the supine position for a minimum of 5 minutes prior to the recording)
- Review adverse events prior to study drug administration, report AEs related to protocol mandated procedures and all SAEs. After drug administration, report all AEs and SAEs.
- Review Concomitant Medications

- Sample Collection For:
  - Safety laboratory tests (hematology, chemistry, and coagulation)
  - HBV genotype for Groups 1-3 and 5 only, for Group 4 historic genotype should be documented in EDC if available
  - Quantitative plasma HBV DNA
  - Quantitative serum HBsAg, CCI [REDACTED]
  - Qualitative HBV serology (HBeAg [reflex HBeAb if HBeAg is negative] and HBsAg [reflex HBsAb if HBsAg is negative])
  - Collection of PBMC, whole blood, serum, and plasma samples for biomarker analysis (PBMC sample collection is only required at the sites that have access to PBMC processing laboratory).
  - Serum sample for HBV viral sequencing (resistance surveillance) or ddPCR (Group 4)
  - Other laboratory tests: urinalysis, urine drug screen and pregnancy test for child bearing potential only)

CCI [REDACTED]

- Estimated creatinine clearance (using Cockcroft-Gault method)
- Randomization
- Drug Administration of GS-9992 and TAF
  - Dispense study drug as directed by IWRS
  - Instruct the subject on the packaging, storage, and administration of study drugs
  - Observe the subject taking the first dose of study drug(s)

**6.3. Post-Day 1 Assessments (Weeks, 1, 2, 4, 8, 12, 16, 24, 36, and 48, All Visits Have Window of  $\pm$  3 Days)**

- Vital signs
- Weight at Weeks 12 and 48
- Review adverse events

- Review concomitant medications
- Complete Physical Examination (Week 12)
- Symptom-directed physical examination
- 12-lead ECG (Subjects must rest quietly in the supine position for a minimum of 5 minutes prior to the recording) (Week 12)
- Sample collection for:
  - Safety laboratory tests (hematology and chemistry; coagulation on Week 12 only)
  - Quantitative plasma HBV DNA
  - Quantitative serum HBsAg, CCI [REDACTED]
  - Qualitative HBV serology (HBeAg [reflex HBeAb if HBeAg is negative] and HBsAg [reflex HBsAb if HBsAg is negative]) at Weeks 12, 24, 36, and 48
  - Collection of PBMC, whole blood, serum, and plasma samples for biomarker analysis at Weeks 1, 4, 12, 24, 48 (PBMC sample collection is only required at the sites that have access to PBMC processing laboratory).
  - Serum sample for HBV viral sequencing (resistance surveillance) or ddPCR (Group 4)
  - Single plasma PK sample will be collected at each on- study treatment visit.
    - On Weeks 2 and 8, the sample will be collected between 15 minutes and 4 hours post-dose. In-clinic dose of GS-9992 required.
    - All PK samples will be collected anytime on all other on-treatment visit.
    - Single PK blood samples will only be collected through Week 12 for Group 4
  - Urine pregnancy test (females of child bearing potential only)
  - Urinalysis
  - Estimated creatinine clearance (using Cockcroft-Gault method) at Weeks 12 and 48

[REDACTED]

[REDACTED]

- Perform study drug accountability (Groups 1, 3, and 5: GS-9992 Weeks 1-12, TAF Weeks 1-48; Group 2 TAF Weeks 1-48; and Group 4: GS-9992 Weeks 1-12)
- Dispense study drug GS-9992 Weeks 4-8 (Groups 1, 3, 4, and 5), TAF Weeks 4-36 (Group 1, 2, 3 and 5) as outlined in [Appendix 2](#).

CCI

**6.5. 24-Week Treatment Free Assessments ( Weeks 4, 8, 12, 16, 20, and 24, All Visits Have Window of  $\pm$  5 Days)**

Subjects that meet the criteria for the treatment free follow-up (Section 3.2) will be followed for 24 weeks or until the initiation of alternative CHB therapy, whichever comes first.

The following assessments will be completed:

- Complete Physical examination at Week 4
- Symptom-directed physical examination
- Review adverse events at Week 4 and collect SAEs through the end of study
- Review concomitant medications
- Vital signs
- Sample collection for:
  - Safety laboratory tests (hematology and chemistry)
  - Quantitative plasma HBV DNA
  - Quantitative serum HBsAg, CCI
  - Qualitative HBV serology (HBeAg [reflex HBeAb if HBeAg is negative] and HBsAg [reflex HBsAb if HBsAg is negative]) to be collected at Weeks 12 and 24

- Collection of PBMC, whole blood, serum, and plasma samples for biomarker analysis at Weeks 4, 8, 12, and 24 (PBMC sample collection is only required at the sites that have access to PBMC processing laboratory).
- Serum sample for HBV viral sequencing (resistance surveillance) or ddPCR (Group 4)
- Urine pregnancy test (females of child bearing potential only at Week 4)

#### **6.6. Assessments for Early Discontinuation from the Study**

If a subject discontinues study dosing (for example, as a result of an AE), every attempt should be made to keep the subject in the study and continue to perform the required study-related follow-up and procedures (see Section 6.5 Post-Treatment Assessments).

If this is not possible or acceptable to the subject or investigator, the subject may be withdrawn from the study.

Criteria for study treatment discontinuation and Toxicity Management can be found in Section 6.11 and Section 7.6.

The Early Discontinuation (ED) Visit should be performed within 14 days from notification of study discontinuation. The following assessments will be performed at the ED visit:

- Vital signs
- Review AEs and concomitant medications
- Complete Physical Examination
- Body Weight
- 12-lead ECG (Subjects must rest quietly in the supine position for a minimum of 5 minutes prior to the recording)
- Sample collection for:
  - Safety Laboratory Tests (hematology, chemistry, and urinalysis)
  - Quantitative plasma HBV DNA
  - Quantitative serum HBsAg, CCI
  - Qualitative HBV serology (HBeAg [reflex HBeAb if HBeAg is negative] and HBsAg [reflex HBsAb if HBsAg is negative])
  - Estimated creatinine clearance (using the Cockcroft-Gault method)

- Serum sample for HBV viral sequencing (resistance surveillance) or ddPCR (Group 4)
  - Single Plasma PK sample
  - Urine pregnancy test (females of child bearing potential only)
  - Collection of PBMC, whole blood, serum, and plasma samples for biomarker analysis (PBMC sample collection is only required at the sites that have access to PBMC processing laboratory).
- GS-9992 and TAF accountability, as applicable

## **6.7. Unscheduled Visits**

The assessments at the unscheduled visits are at the investigator's discretion.

## **6.8. Study Procedure Details**

### **6.8.1. Medical History**

Medical history will include details regarding illnesses and allergies, date(s) of onset, and whether condition(s) is currently ongoing; history of prior and current use of nicotine or nicotine-containing products, alcohol and illegal drugs; and history of current and prior (within previous 30 days) medication; and all prior medication administered to treat HBV.

### **6.8.2. Complete Physical Examination**

A complete physical examination must include source documentation of general appearance, and the following body systems: Head, neck and thyroid, eyes, ears, nose, throat, mouth and tongue; chest (excluding breasts); respiratory; cardiovascular; lymph nodes, abdomen; skin, hair, nails; musculoskeletal; neurological. At the screening visit, the Complete Physical Examination will include documentation of subject height.

### **6.8.3. Electrocardiogram Assessment**

Subjects should rest quietly in the supine position for a minimum of 5 minutes prior to each scheduled ECG acquisition and should remain in that position until the recording is complete. There should be no environmental distractions (including TV, radio, video games, and conversation) while the subjects are resting prior to and during the recordings.

Electrocardiograms will be recorded using the site's standard ECG equipment. All ECGs will be obtained using instruments that analyze data using the same algorithms and produce the same data for interpretation. Electrode placement will be performed according to the method of Wilson, Goldberger, and Einthoven with a check to confirm that the aVR lead is not inverted.

The investigator or other qualified individuals at the study center will review ECGs to assess for changes in ECG intervals and morphology as compared with pretreatment ECGs. ECG interval measurements output by the machine will be used for bedside safety monitoring.

Collection of additional ECGs for routine safety monitoring at additional time points or days is at the discretion of the investigator based on GCP.

QTc interval will be reported using Fridericia's correction:  $QTcF = QT/RR^{0.33}$

#### **6.8.4. Vital Signs**

Assessment of vital signs will include measurement of resting blood pressure, pulse, respiratory rate, and oral temperature. Subject body weight will be obtained at: Screening, Baseline, Weeks 12 and 48, and ED.

Blood pressure will be measured using the following standardized process:

Subject should sit for  $\geq 5$  minutes with feet flat on the floor and measurement arm supported so that the midpoint of the manometer cuff is at heart level.

Use a mercury sphygmomanometer or automatic blood pressure device with an appropriately sized cuff with the bladder centered over the brachial artery.

Measure and record the blood pressure to the nearest 2 mmHg mark on the manometer or to the nearest whole number on an automatic device.

#### **6.8.5. Clinical Laboratory Tests/Assessments**

Blood and urine samples for safety evaluations will be collected throughout the study as outlined in [Appendix 2](#).

##### **6.8.5.1. Blood Sampling**

Blood samples will be collected for the following laboratory analyses:

- Hematology:
  - Hematocrit, hemoglobin, platelet count, red blood cell (RBC) count, white blood cell (WBC) count with differential (absolute and percentage), including lymphocytes, monocytes, neutrophils, eosinophils, basophils, and mean corpuscular volume (MCV), and
- Coagulation panel
  - Prothrombin time, partial thromboplastin time [PTT] and international normalized ratio [INR])

- Chemistry:
  - Alkaline phosphatase, AST, ALT, total bilirubin, direct and indirect bilirubin, total cholesterol, high-density lipoprotein (HDL), low-density lipoprotein (LDL), triglycerides, total protein, albumin, lactic acid dehydrogenase (LDH), creatine kinase (CK), bicarbonate, blood urea nitrogen (BUN), calcium, chloride, creatinine (see below), glucose, phosphorus, magnesium, potassium, sodium, uric acid, and lipase (reflex amylase testing is performed in subjects with total lipase  $>1.5 \times$  upper limit of normal [ULN])
- Serum pregnancy test (females of childbearing potential only)
- Follicle-stimulating hormone (FSH) testing (For female subjects post-menopausal for less than two years, if FSH  $< 40$  mIU/ mL a serum pregnancy test will be required)

#### 6.8.5.2. Urine Samples

Urine samples will be collected for urinalysis and drug screen assessments and urine pregnancy as applicable.

#### 6.8.5.3. Creatinine Clearance

##### Creatinine Clearance

Weight will be collected at screening and upon admission calculate creatinine clearance ( $CL_{cr}$ ) for inclusion criteria.

Creatinine clearance is calculated by the Cockcroft-Gault equation {[Cockcroft 1976](#)} using actual bodyweight (BW).

$$\text{Male: } CL_{cr} (\text{mL}/\text{min}) = \frac{[140 - \text{age (years)}] \times \text{BW}(\text{kg})}{72 \times S_{cr}}$$

$$\text{Female: } CL_{cr} (\text{mL}/\text{min}) = \frac{[140 - \text{age (years)}] \times \text{BW}(\text{kg}) \times 0.85}{72 \times S_{cr}}$$

$S_{cr}$  = serum creatinine (mg/dL)

#### 6.8.5.4. HIV, HDV, and HCV Reflex Testing

In the event of a positive result for serology and/or antigen testing for HIV, HDV or HCV serology, reflex tests will automatically be performed.

Co-infection with HIV, HDV, or HCV is exclusionary.

#### **6.8.6. Adverse Events/Concomitant Medications/Protocol Restrictions**

Evaluation for AEs, review of concomitant medications, and review of protocol restrictions will occur at the times shown in [Appendix 2](#). See [Section 7](#) for more information regarding AEs and [Section 5.4](#) for more information about concomitant medications.

CCJ

#### **6.10. Assessments for Premature Discontinuation from Study**

If a subject discontinues study dosing (for example, as a result of an AE), every attempt should be made to keep the subject in the study and continue to perform the required study-related follow-up and procedures (see [Section 6.11](#), Criteria for Discontinuation of Study Treatment). If this is not possible or acceptable to the subject or investigator, the subject may be withdrawn from the study.

#### **6.11. Criteria for Discontinuation of Study Treatment**

GS-9992 and/or TAF may be discontinued if the following instances are met:

- A confirmed  $\geq$  Grade 3 AE (excluding isolated ALT elevations) considered related to GS-9992 and/or TAF by the investigator, should discontinue one or both study drug(s)
- A confirmed, clinically significant lab abnormality  $\geq$  Grade 3 (excluding isolated ALT elevations) considered related to GS-9992 and/or TAF by the investigator, should discontinue one or both study drug(s)
- Intercurrent illness that would, in the judgment of the investigator, affect assessments of clinical status to a significant degree
- Unacceptable toxicity or toxicity that, in the judgment of the investigator, compromises the ability to continue study-specific procedures or is considered to not be in the subject's best interest
- HBsAg loss confirmed at least 12 weeks apart
- Subject requests to discontinue for any reason
- Subject noncompliance
- Pregnancy during the study
- Discontinuation of the study at the request of Gilead, a regulatory agency or an institutional review board or independent ethics committee (IRB/IEC)

For Group 5, study treatment(s) will be held in all subjects in the dosing group, if  $\geq 3$  subjects experience a Grade 3 adverse event or  $\geq 2$  subjects experience a Grade 4 or serious adverse event, in the same system organ class (excluding isolated ALT elevations) that is considered related by the investigator(s) to the Graded toxicity. Decisions to reinstate continuation of dosing of study treatment(s) will be made by Gilead Medical Monitor upon review of all safety data generated by subjects dosed to date.

Refer to Section 7.6 for additional discontinuation criteria for Toxicity Management.

HBV will be managed according to local standard of care if subjects are discontinued from the study. Subjects that discontinue all HBV therapy should be followed for 24 weeks or until the initiation of alternative CHB therapy, whichever comes first.

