### 3.2. Study Design

This is a randomized, open label study to evaluate the antiviral activity of GS-9992 plus TAF or commercially available NUC. Subjects will be randomized in a 3:1 ratio to Group 1 and Group 2. Randomization will be stratified by HBeAg positive or negative status with approximately 40% of subjects enrolled with HBeAg negative status.

Groups 3, 4, and 5 treatment will be assigned. Group 3 will not start enrolling subjects until the ACHIEVE (SB-9200-HBV-201) trial's independent Data Safety Monitoring Board has deemed it safe to proceed based on review of data for the 200 mg monotherapy cohort.

Group 5 will not start enrolling subjects until safety of the first 12 weeks of the combination treatment in Group 3 has been confirmed by the Medical Monitor.

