### **7.2.1. Assessment of Causality for Study Drugs and Procedures**

The investigator or qualified subinvestigator is responsible for assessing the relationship to each IMP therapy using clinical judgment and the following considerations:

- **No:** Evidence exists that the adverse event has an etiology other than the IMP. For SAEs, an alternative causality must be provided (e.g., pre-existing condition, underlying disease, intercurrent illness, or concomitant medication).
- **Yes:** There is reasonable possibility that the event may have been caused by the investigational medicinal product.

It should be emphasized that ineffective treatment should not be considered as causally related in the context of adverse event reporting.

The relationship to study procedures (e.g., invasive procedures such as venipuncture or biopsy) should be assessed using the following considerations:

- **No:** Evidence exists that the adverse event has an etiology other than the study procedure.
- **Yes:** The adverse event occurred as a result of protocol procedures, (e.g., venipuncture)

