**Table 7-2. TAF Dose Modification and Monitoring**

Liver Toxicity	Action
Confirmed ALT levels $\geq 10 \times$ ULN, with evidence of hepatic toxicity, defined as any one of the following: 
 
• Total bilirubin <math>> 2 \times</math> baseline or nadir AND <math>> \text{ULN}</math> in the absence of Gilbert's disease
 
• Elevated INR <math>> 0.5</math> above baseline AND <math>> \text{ULN}</math>
 
• Abnormal serum albumin <math>> 1 \text{ g/dL}</math> decrease from baseline
 
	Discuss with the Medical Monitor if TAF should be discontinued, unless the safety of the subject is of immediate concern. Subject should be monitored weekly as long as ALT, total bilirubin and INR values remain elevated or above baseline values. If the ALT values remain persistently elevated, the investigator should discuss with the Medical Monitor if TAF should be discontinued.
Confirmed ALT levels $\geq 10 \times$ ULN, without evidence of hepatic toxicity, as defined above	Continue TAF and monitor weekly until ALT values return to normal or baseline levels. If the ALT values remain persistently elevated, the investigator should discuss with the Medical Monitor if TAF should be discontinued.

Specific toxicity discontinuation criteria in Section 6.11 supersede below general toxicity guidelines, and in general, where discrepancy is present, the more conservative criteria apply. The Gilead Medical Monitor should be consulted prior to study drug discontinuation when medically feasible.

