#### **7.6.3. Grade 4 Laboratory Abnormality or Clinical Event**

- For a Grade 4 clinical event or clinically significant Grade 4 laboratory abnormality confirmed by repeat testing that is considered related to investigational medicinal product, investigational medicinal product should be permanently discontinued and the subject managed according to local practice. The subject should be followed as clinically indicated until the laboratory abnormality returns to baseline or is otherwise explained, whichever occurs first. A clinically significant Grade 4 laboratory abnormality that is not confirmed by repeat testing should be managed according to the algorithm for the new toxicity grade.
- Investigational medicinal product may be continued without dose interruption for a clinically non-significant Grade 4 laboratory abnormality (e.g., Grade 4 CK after strenuous exercise, or triglyceride elevation that is non-fasting or that can be medically managed) or a clinical event considered unrelated to investigational medicinal product.

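### Read literally, the Group 5 hold rule misses two non-serious Grade 3 subjects plus one Grade 4 subject in an organ class, although three Grade 3 subjects trigger it

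*Protocol*

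**What the plan says.** Protocol Section 6.11 contains one group-level dosing rule. It applies to Group 5 and appears with the same thresholds in the synopsis, under the criteria for discontinuing study drug. Treatment is held in the whole group when either limb is met:

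- **First limb:** at least three "subjects experience a Grade 3 adverse event or" (the last word leads into the second limb).
- **Second limb:** at least two "subjects experience a Grade 4 or serious adverse event, in the same system organ class (excluding isolated ALT elevations").

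A relatedness condition covers both limbs: "that is considered related by the investigator(s) to the Graded toxicity". The Medical Monitor decides on restart.

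The subject-level criteria in the same section are worded differently. There a greater-than-or-equal sign stands in front of "Grade 3 AE (excluding isolated ALT elevations) considered related to GS-9992 and/or TAF by the investigator". Section 8.6.2 also uses the cumulative form (Grade 3 or higher) for the adverse event summaries.

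Other provisions that bear on the point:

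- Section 7.2.2 keeps severity grade and seriousness apart; a Grade 4 event is not automatically serious.
- Section 7.6.3 covers a related Grade 4 event in the individual: "investigational medicinal product should be permanently discontinued and the subject managed according to local practice". Section 7.6.2 withholds drug for a related Grade 3 event.
- Section 7.6, after Table 7-2, states that "where discrepancy is present, the more conservative criteria apply".
- Section 3.2 delays Group 5 enrolment "until safety of the first 12 weeks of the combination treatment in Group 3 has been confirmed by the Medical Monitor".

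**The concern.** A stopping rule should be monotone in severity: making one event worse should never remove a hold. On its literal wording this rule fails that test for one pattern of counts. The first limb counts Grade 3 subjects and the second counts Grade 4 or serious subjects. Nothing says that a Grade 4 subject also counts towards the first limb.

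The rule matters because Group 5 goes beyond existing experience. Section 1.4.1 reports 400 mg for 7 or 12 days, doses more than twice 400 mg for 7 days, and 12-week dosing only up to 200 mg. Group 5 receives 400 mg for 12 weeks. Section 1.5 relies on pre-defined stopping rules in its benefit/risk argument, and this is the only rule that automatically stops dosing across a group.

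The relatedness clause has a smaller wording fault: it ties the event to the graded toxicity and not to a drug.

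**Working it through.** The plan gives no operating characteristics for this rule, so there is no stated figure to reproduce.

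**Inputs.** The thresholds 3 and 2 are from Section 6.11, and n = 30 for Group 5 is from Section 5.3. Event rates are assumptions, because the documents give none by organ class at 400 mg.

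**Set-up.** Consider related events in one organ class, excluding isolated ALT elevations. Put each subject in at most one category: non-serious Grade 3 (count A, rate a), serious Grade 3 (S, s), Grade 4 whether serious or not (G, g), serious below Grade 3 (B, b).

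- As written: hold if A + S ≥ 3 or S + G + B ≥ 2.
- With Grade 3 or higher in the first limb: hold if A + S + G ≥ 3 or S + G + B ≥ 2.

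**Direct comparison.**

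- Three non-serious Grade 3: first limb 3, hold.
- Two non-serious Grade 3 and one Grade 4: first limb 2, second limb 1, no hold. A serious Grade 4 event does not change this, since that subject still counts once.
- The same, but with one of the Grade 3 events serious: second limb 2, hold.

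Enumerating all counts up to 30 subjects, the two versions differ at exactly one point: (A, S, G, B) = (2, 0, 1, 0).

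**How long the gap lasts.** From that point, one more Grade 3 subject brings the first limb to 3. One more Grade 4 or serious subject brings the second limb to 2. Any further qualifying subject therefore triggers the hold.

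**Size.** The gap in hold probability is the multinomial probability of that point:

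30!/(2! 1! 27!) × a² × g × (1 − a − s − g − b)^27 = 12180 × a² × g × (1 − a − s − g − b)^27

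Example at a = 0.02, g = 0.01, s = b = 0: 12180 × 0.0004 × 0.01 × 0.97^27 = 0.0487 × 0.439 = 0.0214.

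| Non-serious Grade 3 | Grade 4 | Serious Grade 3 | Hold, as written | Hold, revised | Gap (points) |
|---|---|---|---|---|---|
| 0.5% | 0.2% | 0 | 0.0021 | 0.0026 | 0.05 |
| 1% | 0.5% | 0 | 0.0132 | 0.0172 | 0.4 |
| 2% | 1% | 0 | 0.0572 | 0.0786 | 2.1 |
| 5% | 1% | 1% | 0.3311 | 0.3741 | 4.3 |
| 5% | 2% | 0 | 0.2882 | 0.3741 | 8.6 |
| 6.7% (2/30) | 3.3% (1/30) | 0 | 0.5090 | 0.6139 | 10.5 (maximum) |

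At given rates these are upper bounds on the difference in whether a hold ever occurs. They assume exclusive categories, and a Grade 4 subject with a separate Grade 3 event in the same class would count in both limbs. They are end-of-study figures: a group that passes through the gap and then has a further qualifying subject holds late, and is counted as a hold under both versions.

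**The case against.** **The protective reading.** A sensible investigator may take Grade 3 as a minimum. The rule sets a lower threshold for worse events, so leaving a Grade 4 subject out of the Grade 3 count defeats its purpose. The more-conservative sentence in Section 7.6 leans the same way. This stands as a reason to call the point a wording correction. It does not remove it: the same section writes the cumulative form where it means it, and the Section 7.6 sentence chooses between conflicting criteria, while there is no second group-hold rule for it to choose.

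**Other protections.** Group 3 safety is confirmed before Group 5 enrols. Subjects with related Grade 3 or Grade 4 events stop or interrupt drug under Sections 6.11, 7.6.2 and 7.6.3. The Medical Monitor should be consulted before discontinuation when feasible, so would normally know of all three cases. The sponsor can suspend enrolment (Section 6.1), ask for discontinuation (Section 6.11) or end the study (Section 9.3.4). All of this stands and shrinks the consequence. A reader might infer that the gap leaves the cohort unprotected; the documents do not support that. What is missing is only the automatic hold for the remaining subjects.

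**The rates.** The larger gaps rest on assumed rates. Section 1.2.2 reports only mild to moderate treatment-emergent events at 25 to 200 mg. Section 1.3.2 reports 0.7% related Grade 3 or 4 events with TAF across all classes, and no Grade 4 events. This stands: 10.5 points is a mathematical maximum and not an expected loss.

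**The relatedness clause.** A reader might infer that drug-relatedness was left undefined. Section 7.2.1 makes the investigator responsible for "assessing the relationship to each IMP therapy using clinical judgment", so the intent is evident and only the wording needs repair.

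**Conclusion.** The point holds as a minor safety-wording correction. On its literal wording the rule is not monotone in severity grade, at one count pattern: two non-serious Grade 3 subjects and one Grade 4 subject in the same organ class. It requires that events are judged related, that they are not isolated ALT elevations, and that the Grade 4 subject has no separate Grade 3 event in that class. The effect is a group-wide hold missed until one further qualifying subject occurs.

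At rates like those reported so far the gap is negligible (0.05 points at 0.5% and 0.2%). It is about 2 points at 2% and 1%, and at most about 10.5 points, so it matters only if 400 mg proves clearly more toxic.

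A reader might also infer that the thresholds 3 and 2 are wrong, or that the rule fails more widely. The enumeration does not support this: measured against a Grade 3 or higher first limb, only one pattern differs. A parallel pattern, two non-serious Grade 3 subjects plus one subject with a serious Grade 1 or 2 event, also triggers no hold. That is not a severity-grade inversion, because the protocol treats grade and seriousness separately. SAP Section 6.4 records that GS-9992 development was stopped; this bears on the occasion for an edit and not on whether the wording is faulty.

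**What to change.** Make two edits, each in Section 6.11 and in the synopsis:

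1. First limb: at least three subjects with a *Grade 3 or higher* adverse event. Leave the second limb and the thresholds 3 and 2 unchanged.
2. Relatedness clause, shared by both limbs: replace "that is considered related by the investigator(s) to the Graded toxicity" with wording that the events are considered *related to GS-9992 and/or TAF by the investigator(s)*.

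After the first edit, raising the grade of an event can no longer remove a hold. The pattern with a serious Grade 1 or 2 event still triggers none; covering it would be a separate decision.

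The cost is one sentence in two places and somewhat more frequent holds: the increase equals the gap, from 0.05 to at most about 10.5 points over the assumed rates. The Medical Monitor can review each hold and restart dosing.
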